The *Framework for Understanding Effortful Listening* (FUEL) can be used to illustrate how listeners may engage in effortful listening by allocating more cognitive resources to meet the demands imposed during listening in challenging conditions (such as when an individual has hearing loss and/or there is noise)^{29,30}. Importantly, when some cognitive resources are diverted to listening, the remaining cognitive resources may be insufficient for listeners to rapidly or accurately comprehend or remember what was heard. The same logic can easily be applied to effortful viewing/reading to explain why the presence of central visual impairment has repeatedly been shown to reduce reading speed^{31,32}, specifically because processing of visual information in the retinal periphery is slower and not as efficient as in the macular region³³, in both younger and older observers³⁴. In addition, low vision affects eye movements during reading, thereby shrinking the perceptual window where letters are processed, likely due to the increase in the cognitive demand³⁵.

Low Vision (LV) Rehabilitation Reduces Reading Effort

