Recent evidence suggests that visual field loss is associated with neuroanatomical changes in the brain, offering some interesting insights on vision-related brain plasticity. For instance, peripheral vision loss was associated with cortical thickness (CT) decrease in dorsal area V3d, early visual cortex (V1&2) and ventral area V4, while central vision loss was associated with CT decrease in V3d and V3A⁵⁴. The mechanisms responsible for these changes, however, remain unclear. Prins et al.⁵⁵ showed that there was a decrease in gray matter volume in the bilateral superior lateral occipital cortices in a group of monocular blind patients when compared to a group of healthy controls, but that there were no volumetric differences in their visual cortex. These results are consistent with a functional deprivation hypothesis, rather than a trans-synaptic degeneration hypothesis, since the superior lateral occipital cortices play an important role in depth perception, and early visual cortex was spared⁵⁵. Another study compared CT in 10 patients with macular degeneration (MD) to healthy controls⁵⁶. Despite the small sample size, results indicated that MD participants had significantly reduced CT in centrally-responsive primary visual cortex, but interestingly that they had increased CT in peripherally-responsive primary visual cortex. This suggests that compensatory recruitment of spared peripheral vision may induce cortical thickening in specific areas of the visual cortex⁵⁶, a finding that would support the idea of improved function (e.g., reading) using the peripheral retina for reading after the development of AMD. Taken together, these results highlight the potentially important mechanisms of brain plasticity following visual loss, but they need to be replicated using a larger sample. Importantly, these results also open the crucial question of whether vision rehabilitation therapy may induce even more important changes in brain plasticity. To our knowledge, this question has never been addressed before. Therefore, the general **neuroimaging objectives** of this project will be 1) to investigate if visual impairment is associated with reduced cortical thickness in specific cortical areas at baseline (cross-sectional portion), and if vision rehabilitation will result in changes in cortical thickness after 12 months (longitudinal portion).

Does Reduced Reading Effort allow for Increased Reading Activity, Leading to Improved memory/cognition?

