Pilot data from our currently funded FRQS project focusing on cognition and AMD indicate correlations between sensory and cognitive variables in the expected directions insofar as individuals with faster reading speeds demonstrated better scores on the Montreal Cognitive Assessment^{57,58}. Given the information reviewed above, the logical direction for our investigation into the functional connection between LV and cognition is to examine the possible effects of reading rehabilitation on the cognitive abilities of LV patients over time. In order to dis-entangle the effects of visual and cognitive impairments in older adults, members of this research team have adapted cognitive tests so they can be administered to individuals with low vision^{59,60}. In parallel, we are also in the process of developing a vision-screening test that can be administered to individuals with various levels of cognitive impairment^{61,62}. This investigation will guide our future research efforts into the improvement of service provision in LV rehabilitation for the purpose of increasing the independence and health of older adults living with LV.

[figure not shown]
The objectives are to:

- Evaluate cognitive functioning and memory before, and 6 and 12 months after low vision reading rehabilitation using magnification in AMD patients, compared to those with dual (vision and hearing) impairments, and age-matched controls
- Correlate participant characteristics with all cognitive outcome variables in order to identify potential mediators, moderators or confounders

Hypotheses:

- Measures of reading effort (self-report and objective reading speed) will be statistically significantly reduced after participants have received strategies and tools to facilitate reading.
- Measures of reading behaviour will be negatively correlated with measures of reading effort (e.g., participants who report less effort will read a greater amount, more frequently and for longer)
- Individuals who demonstrate reduced reading effort and improved reading behaviour will demonstrate improved scores on cognitive tests after 6 months of having received rehabilitation strategies and tools, compared to those whose reading effort remains high or whose reading behaviour remains unchanged. These beneficial effects will be maintained after 12 months.
- Reading measures correlate with cortical thickness (CT) in the visual cortex;

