Participants: We will recruit 150 new clients (65+ years of age) referred for low vision rehabilitation to either of the two vision rehabilitation centres in Montreal (Lethbridge-Layton-Mackay and INLB, see partner letters of support), and 50 age-matched (by decade) older adults without visual impairment (to be recruited from spouses or family members of participants, as well as through open advertisement through media and senior groups). In addition, we have access to the *Banque des participants* of the *Centre de recherche institut universitaire de geriatrie de Montreal (CRIUGM; n > 1000)*. Within this database, it will be possible to match our control participants on variables such as age, gender, education, and other potential variables of interest such as MoCA score). Client-participants are

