Time 2 – 6-Months and Time 3 – 12-Months Follow-Up: Six and 12 months after the initial rehabilitation appointment, the research assistant will meet with each participant (at home or in the lab, according to their preference) in order to repeat the experimental protocol, and all reading, cognitive and hearing measures will be administered each time. Throughout the period of the protocol, data from the rehabilitation chart will be extracted as it becomes available, with the final data collection concluding after the 12-month follow-up.

Statistical Analysis – Functional measures: To analyze these data, we will examine change in cognitive test scores from baseline over time using mixed-effects regression models, adjusting for level of vision and hearing impairment as fixed or random effects, and compare across sensory group (VI/DSI/Control). The analyses will include consideration of potential moderators or confounders (i.e., gender, age, education). In addition, we will calculate effect sizes, confidence intervals and Bayes Factors for main effects, interactions, and all post-hoc analysis.

When reflecting on the question of a control group we further consulted with the rehabilitation centres and discussed recruitment approaches and limitations; however, for practical and ethical reasons we are not able to withhold rehabilitation services from a possible comparison group, and waiting times are too varied across the centers and seasons of the year to allow for a waiting-list control group. As a result, we are proposing a quasi-experimental repeated-measures design with the intent to let the participants act as their own comparison across time points.

In addition, the data allow us to follow potential **exploratory avenues of analysis:**

- 1) If the recruited participants naturally divide into individuals whose reading effort was reduced and their reading activity has increased, versus those where we do not observe a change in reading behaviour, we can compare these two groups directly (e.g., while still considering their hearing status, or their gender)

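### Hypothesis 2 is worded as a between-person correlation of reading behaviour with reading effort, so differences in vision can satisfy it, and no planned analysis tests whether a fall in effort goes with a rise in reading

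*Combined protocol and SAP*

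**What the plan says.** The hypotheses stand under a heading that asks a causal question about change: "Does Reduced Reading Effort allow for Increased Reading Activity, Leading to Improved memory/cognition". Hypothesis 2 is the middle link of that chain. It reads "Measures of reading behaviour will be negatively correlated with measures of reading effort", with the example that "participants who report less effort will read a greater amount, more frequently and for longer". It gives no time point, no change from baseline, no analysis set and no covariates.

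The neighbouring hypotheses are framed as change. Hypothesis 1 predicts lower effort after rehabilitation and counts objective reading speed among the effort measures. Hypothesis 3 says "Individuals who demonstrate reduced reading effort and improved reading behaviour will demonstrate improved scores on cognitive tests after 6 months".

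Under Statistical Analysis – Functional measures, "we will examine change in cognitive test scores from baseline over time using mixed-effects regression models", adjusted for level of vision and hearing impairment. The outcome of that model is cognition. The section gives no model with reading behaviour as outcome.

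Four other places matter:
- The background on low vision and reading effort says that "the presence of central visual impairment has repeatedly been shown to reduce reading speed".
- The Participants section requires patients to be at 20/60 or worse in the better eye, states no lower limit, and adds "50 age-matched (by decade) older adults without visual impairment".
- The Reading Outcome Measures section names a reading-habit questionnaire, which covers how much and how often a person reads, as the subjective measure of effort.
- Reading measures are repeated at 6 and 12 months.

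Hypothesis 4 has a similar form: "Reading measures correlate with cortical thickness (CT) in the visual cortex".

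**The concern.** A correlation between people answers a different question from the one in the heading. Severity of vision loss plausibly raises effort and lowers the amount read, and by the protocol's own account it slows reading, which Hypothesis 1 treats as an effort measure. Two patients with different acuity can thus produce the predicted pattern although neither would read more if reading became easier. The pattern would be there at Time 1, before any device had been supplied.

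At stake is the mechanism. If the correlation is found, a reader may take it as support for the step from easier reading to more reading, on which the cognitive hypothesis is built. The data for a more direct test are due to be collected, but no analysis is assigned to them.

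**Working it through.** **Plan's own figure.** The documents give no figure for Hypothesis 2. The one sample-size figure, 141, belongs to the 3×3 analysis of variance. It reproduces for the group-by-time interaction with f = 0.15, alpha 0.05 and an assumed correlation of 0.5 between visits: λ = 0.15² × 141 × 3 / (1 − 0.5) = 19.0 on 4 and 276 degrees of freedom, power 0.952. It has no bearing on this point.

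**Is the link tested elsewhere?**
- The mixed models have cognition as outcome.
- Hypothesis 3 and the first exploratory avenue combine effort and behaviour into one grouping and compare cognition.
- The second avenue uses reading measures as covariates for cognition.
- The third is a latent factor analysis of what goes with better cognition or reading ability.
- The imaging section models thickness by group.

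None relates reading behaviour to reading effort.

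**Patients only, one visit.** Suppose vision loss correlates a with effort and −a with behaviour, and nothing else connects them. Then r = −a². By Fisher's z, the chance of a significant negative result (two-sided 0.05) is Φ(atanh(a²) × √(n − 3) − 1.96). With n = 150, √147 = 12.12. The values of a are assumptions.

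| a | r | atanh(a²) × 12.12 | chance, n = 150 | chance, n = 121 |
|---|---|---|---|---|
| 0.3 | −0.09 | 1.09 | 19% | 16% |
| 0.4 | −0.16 | 1.96 | 50% | 42% |
| 0.5 | −0.25 | 3.10 | 87% | 79% |

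The last column allows for two rounds of the planned 10% attrition: 150 × 0.9² = 121.5.

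**Between-person versus within-person.** In 4,000 simulated trials, vision was stable and loaded 0.6 on effort and −0.6 on behaviour, rehabilitation lowered effort, and effort had no influence on behaviour. In patients, the correlation of levels was significantly negative in 99.5% of trials at Time 1 (mean r −0.36) and 99% at Time 2 (−0.33). Change in effort against change in behaviour gave 2.6%, and the vision-adjusted Time 1 correlation 2.8%. The nominal rate per tail is 2.5%.

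**If controls were pooled.** With 150 patients, 50 controls, no within-group association and an equal gap of d SD on both measures, r = −0.1875d² / (1 + 0.1875d²), where 0.1875 = 0.75 × 0.25. For d = 0.5, 0.8, 1.0 and 1.5, r = −0.04, −0.11, −0.16 and −0.30. The chance of significance is 9%, 33%, 61% and 99%. The gaps are assumptions.

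**Is a within-person test enough?** Only if vision is stable. With 10% attrition per visit there are 150 + 135 + 121.5 = 406.5 person-visits. Removing 150 person means and 2 visit terms leaves about 254 degrees of freedom, and √254 = 15.94. If visit-to-visit vision loads 0.3, 0.4 or 0.5 on each measure and effort has no effect, the chances are Φ(1.44 − 1.96) = 30%, Φ(2.57 − 1.96) = 73% and Φ(4.07 − 1.96) = 98%. Simulation agrees within a percentage point, and the rate falls to about 2–3% once vision is in the model.

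**Hypothesis 4.** With 30 patients and 15 controls, an assumed reading gap of 2 SD and a thickness gap of 0.5 to 1 SD, pooling alone gives r = 0.222 × 2 × 0.5 / √(1.889 × 1.056) = 0.16 up to 0.222 × 2 × 1 / √(1.889 × 1.222) = 0.29. At n = 45 this is significant in about 18% to 50% of samples.

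**The case against.** The strongest reply is that Hypothesis 2 is under-specified rather than wrong. It says only that the measures are negatively correlated. A reader might infer an unadjusted correlation pooled over all 200 participants, and with gaps of 1 to 2 SD in effort and 1 SD in behaviour that would put the chance of spurious support at 62% to 97%. The documents do not support that inference:
- The text says neither unadjusted nor pooled.
- Hypotheses 1 and 3, on either side, concern people who have received rehabilitation, and the hypotheses that involve controls name them.
- The Clinical Variables section makes acuity, contrast sensitivity and visual field available for statistical control.
- Gender is to be considered in all analyses.

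This part of the objection stands, and it is why the patient-only figures lead here.

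It is also fair that Hypothesis 2 claims only an association, that participants are meant to serve as their own comparison over time, and that all analysis details are to go into a stage 1 pre-registered report. But the worked example compares people, having vision variables available is not a plan to use them here, and the self-comparison is not carried into any model of reading behaviour. The pre-registered report is a good place for the repair; it does not show that the repair has been made.

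Finally, a within-person model without a vision term could fail in the same way, as the working shows. That objection is accepted and shapes the fix.

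**Conclusion.** The point holds in a limited form. The wording of Hypothesis 2 allows vision alone to satisfy it, including before rehabilitation, and nothing else in the plan tests the within-person link. That conclusion follows from the text. How often it would happen does not: it depends on assumed correlations with vision, and is modest at 0.3 and high at 0.5. Pooling the controls would raise the risk unless the group gaps were small, but pooling is a possibility the text leaves open, not something it states.

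Two further inferences should be resisted. The documents do not say that this correlation will by itself be presented as proof of mechanism. And the weakness does not reach the sample size or the main cognitive model. It is a change worth making to a supporting hypothesis.

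**What to change.** Restate Hypothesis 2 as: *among VI and DSI patients, a fall in reading effort from Time 1 to Times 2 and 3 goes with a rise in reading behaviour.*

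- **Model.** Fit a mixed model of reading behaviour on effort, split into the person mean and the within-person deviation. Add visit, VI/DSI group, baseline vision and, where the chart has it, follow-up vision. The within-person coefficient is the test. Without randomization it remains an association.
- **Measurement.** Specify separate items for effort and behaviour, because the questionnaire named for subjective effort also asks about extent and frequency of reading. Shared items would build in part of the correlation.
- **Cross-sectional correlation.** Report it as descriptive, adjusted for group and vision.
- **Hypothesis 4.** If controls are included, adjust the correlation of reading with thickness for group.

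The cost is one reworded hypothesis and one extra model. Reading data are already due at each visit. Follow-up vision depends on what the charts contain, so its completeness should be reported. The within-person association will probably be smaller than the correlation of levels.

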there is a symbiotic relationship between reading and cognitive processing as has been documented extensively in the psycholinguistics/neurolinguistics, epidemiological and imaging literature^{46,47}. Notably, a number of studies have shown that engaging in high-level cognitive activities, such as reading discourse, appears to preserve cognition. The frequency of participation in activities that are mentally stimulating, such as reading, is associated with lower risk of incident Alzheimer's disease⁴⁷⁻⁴⁹. More recently, studies have also linked reading and engaging in higher-level cognitive activities with increased cognitive reserve, that in turn is associated with more tolerance of AD pathology and stimulation of brain plasticity⁵⁰⁻⁵³.

Structure-Function Relationships

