inferior occipital gyrus, the middle occipital gyrus (and sulcus), the superior occipital gyrus, the cuneus, the lingual gyrus, the occipital pole, and the calcarine sulcus. CT will be investigated more specifically inside visual areas, namely V1 (BA17) – primary visual area, V2 (BA18) – secondary visual area, and V5/MT – visual area, middle temporal, by using an atlas from the Martinos Center for Biomedical Imaging (US) and the Institute of Neurosciences and Biophysics (Germany) (<http://surfer.nmr.mgh.harvard.edu/fswiki/BrodmannAreaMaps>). In order to examine if vision rehabilitation will result in changes in CT, we will examine by calculating percentage difference in extracted CT values for each of the above-mentioned visual regions pre- and post- reading rehabilitation. Differences between groups or between regions pre- and post-intervention will be considered significant at $p < 0.05$ after correction using false discovery rate.

Limitations & Mitigation Strategies:

Given the logistics of having the reading intervention delivered through services that are regulated by the Quebec Ministry of Health, we place our trust in the quality of rehabilitation service delivery without being able to control this aspect of the study; however, we believe that this trust is well deserved, given the quality and type of care provided in Quebec¹¹⁴⁻¹¹⁶. It is likely that a certain number of participants will self-select not to complete the 1-year follow-up or to abandon parts of the recommended intervention tools and techniques. Therefore, we will examine differences in participant characteristics and consider intent-to-treat within the statistical analyses. We expect certain variability in the cognitive status of our participants, as there are no cognitive exclusion criteria. This pragmatic approach to recruitment is chosen intentionally as we speculate that the beneficial effect of reading rehabilitation may become apparent at different levels of magnitude, depending on the cognitive starting point; however, this remains speculation at this point. Our statistical analyses will need to consider this additional source of variability.

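### A positive Hypothesis 3 result would be an association: reading change and cognitive change share one window, so the comparison cannot show which drives which

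*Combined protocol and SAP*

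**What the plan says.** The first study question, in the protocol's opening section, is causal: it asks whether better reading performance improves cognition. The third item under Hypotheses links the two directly: "Individuals who demonstrate reduced reading effort and improved reading behaviour will demonstrate improved scores on cognitive tests after 6 months", "compared to those whose reading effort remains high or whose reading behaviour remains unchanged". Its 12-month statement is about persistence only: "These beneficial effects will be maintained after 12 months".

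Under Data Collection, follow-up takes place "Six and 12 months after the initial rehabilitation appointment", and "all reading, cognitive and hearing measures will be administered each time". Rehabilitation begins within 3 months of Time 1.

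Statistical Analysis – Functional measures plans a mixed-effects regression of cognitive change over time, compared across the three sensory groups, with gender, age and education named as possible moderators or confounders. Two exploratory options then bring in reading change. If participants fall into improvers and non-improvers, "we can compare these two groups directly"; otherwise reading measures enter as covariates.

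Three other passages matter:

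- The Link between Reading and Cognition states that "there is a symbiotic relationship between reading and cognitive processing".
- Limitations & Mitigation Strategies notes that "there are no cognitive exclusion criteria".
- Cognitive Outcome Measures argues that, because testing is auditory, any cognitive gain can be credited to the effect of better visual function on cognitive stimulation.

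**The concern.** Participants are not assigned to improve their reading. They are classified afterwards, from reading change over the interval in which cognitive change is also measured. Three explanations then predict the same difference between improvers and non-improvers: reading improved cognition, better-preserved cognition led to more or easier reading, or something else (general health, for example) moved both. A smaller decline or a larger practice gain among people with better-preserved cognition would be enough.

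Auditory testing removes one alternative, better perception of the test stimuli. It does not address cognition driving reading. The limitations section does not mention direction, and baseline cognition is not among the named confounders. At stake is the wording of the conclusion: a positive Hypothesis 3 result could be reported as evidence that reading rehabilitation benefits cognition when the comparison cannot show it.

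**Working it through.** **1. The plan's own figure, and what it covers.** Sample Size gives n = 141 for a 3×3 within-between ANOVA with effect size 0.15, alpha 0.05 and power 0.95. Taking 0.15 as Cohen's f and assuming a correlation of 0.5 between repeated measures, sphericity and equal groups (none stated):

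- λ = f² × N × m / (1 − ρ) = 0.0225 × 141 × 3 / 0.5 = 19.04
- df = (3 − 1)(3 − 1) = 4 and (141 − 3)(3 − 1) = 276
- power = 0.952; N = 138 gives 0.947

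The figure reproduces. It depends on the assumed correlation (N = 195 at 0.3, 87 at 0.7). It sizes the group-by-time interaction, not Hypothesis 3.

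**2. The shared window.** Time 2 is 6 months after the first rehabilitation appointment, which falls 0 to about 3 months after Time 1. So Time 1 to Time 2 is 6 + 0 to 6 + 3, about 6 to 9 months, for both reading change and cognitive change.

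**3. Number of patients.** With 150 patients and about 10% attrition per time point: 150 × 0.9 = 135 at 6 months and 150 × 0.9² = 121.5 at 12 months.

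**4. Chance of a positive same-window test when reading has no effect on cognition.** By Fisher's z, with r the correlation produced by a non-causal route:

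P(positive) = 1 − Φ(1.96 − atanh(r)·√(n − 3)) + Φ(−1.96 − atanh(r)·√(n − 3)), with n = 135 and √132 = 11.489.

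| Assumed r | atanh(r) × 11.489 | P(positive) |
|---|---|---|
| 0.05 | 0.575 | 0.0886 |
| 0.10 | 1.153 | 0.2107 |
| 0.15 | 1.736 | 0.4117 |
| 0.20 | 2.329 | 0.6440 |
| 0.30 | 3.556 | 0.9448 |

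The documents give no value for r. These rates are the power to detect whatever correlation is assumed.

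**5. Does the same-window result depend on direction?** Simulation with n = 121, 2,000 runs per structure, assumed path strength 0.3 and no measurement error. Entries are the percentage of runs with a significant positive result at two-sided p < 0.05.

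| True structure | Mean r | Correlation | Median-split improvers vs others | Ordered check |
|---|---|---|---|---|
| Reading drives cognition | 0.30 | 92.5% | 76.7% | 89.0% |
| Cognition drives reading | 0.30 | 91.5% | 75.4% | 2.9% |
| Common cause | 0.30 | 92.7% | 77.0% | 2.5% |

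The ordered check is Time 1–2 reading change predicting Time 2–3 cognitive change, given Time 1–2 cognitive change. The same-window analyses cannot tell the three structures apart. At strengths of 0.2 and 0.4 the rates shift, but they remain nearly equal across structures.

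**6. How far ordered models can be trusted.** The separation in step 5 is idealised: it assumes an effect that continues after 6 months and scores without error. Further simulations used persistent individual cognitive slopes that drive reading, no effect of reading, and test reliability of 0.7 to 0.8 (all assumptions). A model of Time 3 cognition on Time 1–2 reading change, given Time 1 and Time 2 cognition, was falsely positive in 44% to 93% of runs, depending on the settings. Requiring the mirror model to be negative as well still gave false support in 2% to 21%. With a real effect complete by 6 months and then maintained, as Hypothesis 3 predicts, the two-model rule supported it in only 12% to 26%. The ordered models are informative but cannot decide direction.

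**The case against.** The strongest reply is that the planned functional analysis is the group-by-time mixed model. It matches the first objective and the 3×3 design, and it does not form groups from reading change after baseline. The reading-change comparisons are labelled exploratory and worded conditionally. This stands. A reader might infer that the trial therefore cannot answer its first question; the documents do not support that, because the direction problem does not touch the main model. But that model does not test Hypothesis 3, which is a stated directional hypothesis with only the exploratory options to test it.

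The plan also anticipates some of this. The limitations section says the analyses must allow for varying cognitive status, the second objective looks for mediators, moderators and confounders, and Study Design commits to a stage 1 pre-registered report. So baseline cognition is foreseen, though no model or covariate is given, and nothing addresses temporal order.

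Two mechanisms should not be pressed as fact. The documents do not say that declining patients learn devices less well. A good or bad test day could move reading speed and cognitive scores together, but it is a weaker explanation for reading behaviour, which comes from a habits questionnaire.

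**Conclusion.** The point holds for Hypothesis 3 and the exploratory analyses that serve it. The structure of the comparison establishes this without any numerical assumption: reading and cognition share the window and the visits, the groups are self-formed, no analysis is time-ordered, and the protocol acknowledges a two-way relation.

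The size is illustrative. For non-causal correlations of 0.05 to 0.30 and about 135 patients, the chance of a positive test runs from about 9% to 94%. It would be wrong to quote the upper end as an expected false-positive rate, since nothing in the documents fixes the correlation. It would also be wrong to infer that ordered models settle direction: measurement error and persistent decline can make either one falsely positive, and an effect complete by 6 months leaves the reading-to-cognition model near zero. This is a correction to what may be concluded and should be made before the stage 1 report is fixed.

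**What to change.** 1. State under Hypotheses and in the functional analysis section that a positive Hypothesis 3 result is an association and does not by itself show that improved reading improved cognition.
2. Limit the attribution sentence under Cognitive Outcome Measures to ruling out better perception of the test stimuli.
3. Adjust the reading-change comparison, in either exploratory form, for baseline cognition, naming the measure in advance. Time 1 scores are already collected; the non-visual MoCA items are one option. This handles starting level, not decline during follow-up.
4. Add two mirror models as sensitivity analyses: (a) Time 1–2 reading change predicting Time 3 cognition, given Time 1 and Time 2 cognition; (b) Time 1–2 cognitive change predicting Time 3 reading, given Time 1 and Time 2 reading. Report both with confidence intervals, and do not use them as a decision rule.
5. State beside them that measurement error and persistent individual decline can make either falsely positive, that an effect complete by 6 months would leave (a) near zero, and that stable confounding by health or motivation remains.

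Cost: analysis-plan wording and two extra models on data already planned. The models have low power, with about 121 patients expected at 12 months, and the causal wording becomes softer.
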